In addition, we will perform univariable analyses and multivariable logistic regression analyses to calculate unadjusted and adjusted odds ratios for acute coronary syndrome. We will take a number of baseline regressors into account including age, sex, GRACE-Score, history of coronary heart disease, atrial fibrillation, heart failure, wall motion abnormalities on echocardiography and ACS-typical changes on ECG.

In an exploratory analysis, we will calculate an optimized multivariable logistic regression model using backward selection. In addition, we plan to calculate the best cut-off of troponin levels to predict acute coronary syndrome using the maximum area under the receiver operating characteristic (ROC) curve. Subgroup analyses will be defined in the statistical analysis plan before the first endpoint analysis is performed.

Interim analyses

In order to assess safety of the study, we will perform an interim analysis of the occurrence of serious adverse events of special interest (SAESI, see below) after inclusion of 100 and 200 patients, respectively. This analysis will be used by the DSMB to consult the Steering Committee concerning the continuation or premature termination of the study due to safety concerns.

Methods against bias

PRAISE is a multicenter observational study. Recruiting sites are stroke centers in Germany. The diagnosis of “acute ischemic stroke” will be established by experienced neurologists. ECG, echocardiography and coronary angiography will be performed by experienced cardiologists according to SOPs. All study examinations will be re-assessed by blinded core laboratories (see above). Since troponin will be measured by the recruiting study sites before study inclusion using different assays, troponin will also be re-measured at a core laboratory ([name], UKE Hamburg) using the same biosamples. The primary endpoint will be adjudicated by an independent endpoint adjudication committee, which will be blinded to patients’ troponin levels. The assessment of functional and cognitive outcome will be performed using standardized scores (see above).

The primary hypothesis that has been described in this protocol will be tested in an intention-to-diagnose analysis in order to prevent possible selection bias. A per-protocol-analysis is planned as a secondary analysis.

[figure not shown]
Study timeline:

Fig. 1: study timeline

Ethical considerations:

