3.2 Adherence and protocol deviations

Adherence is not relevant in this study, since there is no therapeutic intervention for study purposes to be followed.

All protocol violations will be documented and classified as major or minor in a blinded manner by an independent staff member who is not involved in the study process.

A major protocol deviation occurs if contrary to the study protocol a patient could not receive a coronary angiography. The following reasons are listed:

- Data from coronary angiography are not provided for technical reasons.
- Patient refuses coronary angiography.
- Clinician declines coronary angiography for medical reasons.
- Coronary angiography is not performed for capacity reasons.
- A transfer of images from the ultrasound scanner is not possible for technical reasons.

Further, a major protocol deviation occurs if a troponin measurement is not available.

These patients will not be taken into regard into the primary analysis.

A minor protocol deviation occurs if a patient could not receive echocardiography. The following reasons are listed:

- Based on clinical indication, a transesophageal echocardiography is performed, which is not relevant for the objective of this trial.
- Echocardiography is not performed for capacity reasons.

Patients with minor protocol deviations are included in the primary analysis.

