3.3 Analysis populations

3.3.1 Modified Intention to diagnose Population (mITD)

The primary analysis population is the mITD (intention to diagnose) population. The mITD population consists of all patients in whom troponin measurements at 0 and 3 hours were available.

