3.3.2 Per Protocol population (PP)

The Per Protocol population includes all patients who have no major protocol violation. In particular coronary angiography must have been performed.

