5.1 Analysis methods

5.1.1 Primary endpoint

The primary outcome analysis will be performed in the mITD population using the adjudicated endpoint data of the endpoint adjudication committee.

The presence/absence of ACS in relation to presence/absence of dynamic troponin elevation (defined as rise/falling pattern of >50% (Δ -change at 0 vs. 3 hrs)) will be analysed by calculation of the diagnostic odds ratio together with the 95%-confidence interval. Corresponding p-value will result from the likelihood ratio chi-square test.

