5.3 Additional analyses

The primary outcome analysis is repeated in the PP population. Additional analyses of the presence/absence of ACS in relation to presence/absence of dynamic troponin elevation include the calculation of further diagnostic accuracy measures like sensitivity and specificity together with the 95%-confidence interval.

A mediation analysis will be conducted to identify direct and indirect effects of the diagnostic group (dynamic vs. stable) and additionally peak troponin T in patients with available troponin T values (exposure variables) and the presence of ACS (yes vs. no) as well as presence of MI type 1 (yes vs. no) and in patients with ACS MI (Type 1 vs. Type 2) (mediator variables) on mortality and MACE (target outcome) using accelerated failure time models. This will be performed after unblinding of the diagnostic groups and analysed in an explorative manner.

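### SAP 3.2 does not say which major deviators leave the primary analysis; read as all of them, it removes patients without coronary angiography whom SAP 3.3.1 and 5.1.1 keep in

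*SAP*

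**What the plan says.** SAP 3.2 first lists the ways in which angiography can be missing: data not provided, patient refusal, clinician decision, lack of capacity, or images that cannot be transferred. It then adds an unavailable troponin measurement as a further major deviation. A separate sentence follows: "These patients will not be taken into regard into the primary analysis". After describing minor deviations (no echocardiography), the section closes with "Patients with minor protocol deviations are included in the primary analysis".

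The sections that define the analysis sets read differently. SAP 3.3.1: "The mITD population consists of all patients in whom troponin measurements at 0 and 3 hours were available". SAP 5.1.1: "The primary outcome analysis will be performed in the mITD population using the adjudicated endpoint data of the endpoint adjudication committee". Neither mentions angiography. That requirement appears in SAP 3.3.2, for the per-protocol (PP) set: "In particular coronary angiography must have been performed". SAP 5.3 then adds: "The primary outcome analysis is repeated in the PP population".

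The protocol (Methods against bias) says that the primary hypothesis "will be tested in an intention-to-diagnose analysis in order to prevent possible selection bias", and continues: "A per-protocol-analysis is planned as a secondary analysis".

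**The concern.** A patient with both troponin values and no angiography is in the primary set under SAP 3.3.1 and 5.1.1. Under SAP 3.2, read as covering all major deviations, the same patient is out. Two analysts working faithfully from the same plan could therefore analyse different patients and report different primary odds ratios.

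The patients in question are not obviously a random subset. Refusal by the patient and a medical decision by the clinician are among the listed reasons. Selection on having had angiography is the sort of selection that the protocol's choice of analysis was meant to avoid. An open choice of primary set is also one that could be settled after results are seen.

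**Working it through.** **1. The plan's own figure.** Inputs from the protocol's sample size calculation: odds ratio about 4, 6% risk in the stable group, 11/29 (38%) dynamic, 80% power, alpha 0.05. SAP 3.1 makes tests two-sided.

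- Dynamic-group risk: 4 × 0.06 / (1 + 3 × 0.06) = 0.24 / 1.18 = 0.203.
- The two-proportion formula with an 18:11 allocation gives 174 in total without continuity correction and 202.5 with it, which rounds up to 203.
- 251 − 203 = 48 patients, and 48/251 = 19.1%. The protocol attributes this reserve to withdrawal of consent.

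The stated 203 reproduces and is not in dispute. It serves below only as a denominator.

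**2. The rules side by side.**

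| Patient | 3.2, all major deviations | 3.2, missing troponin only | 3.3.1 and 5.1.1 (primary) | 3.3.2 (PP) |
|---|---|---|---|---|
| Both troponins, angiography done | in | in | in | in |
| Both troponins, angiography or its data or images missing | **out** | in | **in** | out |
| 0 h or 3 h troponin missing | out | out | out | out |
| Echocardiography missing only | in | in | in | in |

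Only the second row is in conflict, and only under the broad reading. In that column the entries match the PP column in every row, so the PP repeat in SAP 5.3 would return essentially the primary result.

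**3. Which reading the text supports.**

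- For the broad reading: the troponin deviation is joined to the angiography deviations as a further item of the same class, the exclusion sentence follows both, and the section ends with a mirror rule for minor deviations. The contrast drawn is major against minor.
- For the narrow reading: the troponin sentence comes immediately before the exclusion, and this reading gives SAP 3.3.1, 3.3.2, 5.1.1 and 5.3 and the protocol each a distinct function.
- SAP 2.2 does not decide it. It says that angiography is performed in all patients, while SAP 3.2 lists reasons why it might not be.

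**4. Scale.** The documents give no rate of missing angiography, so only a per-5% count is possible (an assumption, for scale): 0.05 × 203 = 10.15 and 0.05 × 251 = 12.55, or about 10 and 13 patients.

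Sampling error for comparison, by Woolf's interval exp(ln 4 ± 1.96 × SE), with SE² the sum of reciprocal cell counts, 77 dynamic and 126 stable patients:

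- 24% (7/29) ACS overall: risks 0.401 and 0.144; cells 30.9, 46.1, 18.1, 107.9; SE 0.344; 95% CI 2.04 to 7.86.
- 6% ACS in the stable group: risks 0.203 and 0.06; cells 15.7, 61.3, 7.6, 118.4; SE 0.470; 95% CI 1.59 to 10.05.

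A modest difference between the two sets would be small against intervals this wide.

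**The case against.** The strongest reply is that this is ambiguity and not contradiction. The sentence on troponin is the nearest antecedent, SAP 3.3.1 and 5.1.1 are the operative sections, and a plan should be read so that every section does some work. On that view SAP 3.2 merely repeats the troponin condition. This stands as a possible reading, and it is why the point is not put as a flat contradiction. It does not remove the problem: the closing rule on minor deviations makes the broad reading at least as natural, and membership of the primary set should not rest on inference.

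A reader might also infer that the SAP has a separate error in giving no primary rule for an mITD patient without an adjudicated endpoint. The documents do not support that. SAP 5.1.1 uses the committee's adjudicated data, and SAP 5.2 labels imputation and best/worst-case replacement as sensitivity analyses, so an unimputed analysis of adjudicated patients is clearly implied. The 5% threshold in SAP 5.2 applies to multiple imputation; none is stated for the best/worst-case analysis. Nor is missing angiography the same as missing adjudication: according to the protocol (Study procedures), the committee also weighs ECG, echocardiography and symptoms, and nothing says that it withholds a verdict without angiography.

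**Conclusion.** The point holds as an ambiguity in a rule that determines the primary analysis set. Under the broad reading, SAP 3.2 conflicts with SAP 3.3.1 and 5.1.1, merges the primary set with the PP set and departs from the protocol's intention-to-diagnose analysis. Under the narrow reading there is no conflict. It should be fixed, because it concerns the single primary analysis and the correction is one of wording.

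No numerical effect is claimed. A reader might infer that excluding these patients biases the odds ratio in a known direction or costs power. Neither follows: no rate of missing angiography is given, and nothing shows which set lies closer to the truth. The count of about 10 per 203 rests on an assumed 5%, and the intervals rest on the planning odds ratio of 4 and the pilot proportions.

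**What to change.** In SAP 3.2, replace the exclusion sentence with:

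> *Patients without both the 0 h and the 3 h troponin value are excluded from the primary (mITD) analysis. Patients with any other major deviation listed above (angiography not performed, angiography data not provided, or image transfer not possible) remain in the mITD set with the committee's adjudicated endpoint where one exists, and are excluded only from the PP set.*

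Report, by dynamic and stable group, how many mITD patients had no angiography and how many had no adjudicated endpoint, and show the PP result beside the primary one.

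As a minor clarification, SAP 5.1.1 could state the implied rule: the primary odds ratio uses mITD patients with an adjudicated endpoint, and the analyses in SAP 5.2 are sensitivity analyses. The 5% imputation threshold need not change.

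The cost is a few lines of text and one table, with no new data. The wording should be settled before the troponin groups are unblinded; the documents do not show whether that point has passed. The downside is that some adjudications in the primary set would rest on ECG, echocardiography and symptoms without angiography, which could shift the odds ratio either way. The PP result has its own selection, so it serves as a contrast and does not prove either figure.

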3.3 Analysis populations

3.3.1 Modified Intention to diagnose Population (mITD)

The primary analysis population is the mITD (intention to diagnose) population. The mITD population consists of all patients in whom troponin measurements at 0 and 3 hours were available.

3.3.2 Per Protocol population (PP)

The Per Protocol population includes all patients who have no major protocol violation. In particular coronary angiography must have been performed.

3.3.3 Evaluated for Safety Set (EFS)

All patients who received a coronary angiography and thus provided at least one troponin measurement will be included into the Evaluated for Safety (EFS) set.

4 Trial Population

4.1 Screening data

The following summaries will be presented for all screened patients:

- The reported number of stroke patients treated at the respective center
- the number and percentage of patients included

This summary will be provided overall and by study center.

4.2 Eligibility

The number of ineligible patients will not be reported.

4.3 Recruitment

All available recruitment information will be included and presented in a flow diagram according to the STARD Statements (Bossuyt, et al. 2003) (see Appendix).

4.4 Withdrawal/follow-up

In case of withdrawal from follow-up this is documented in different levels:

1. Patient says explicitly, that he/she does not want to take part on further phone interview regarding specific score assessments (timing: measurement time point of statement, documentation of reasons for the decision)
2. Patients are not able to attend follow-up examinations due to health issues.
3. Patient says explicitly, that he/she does not want to be contacted in further follow-ups.
4. Patients immediately withdraw consent for study participation after study inclusion.
5. Patients who are subsequently identified as not meeting the inclusion and exclusion criteria will be treated as patients who have withdrawn from the study.

The number by level of withdrawal will be tabulated.

4.5 Baseline patient characteristics

Baseline is defined as the measurement recorded at hospital admission (< 72 h after admission) (“V1”). All relevant characteristics to be measured at baseline are listed in table 1 of the study protocol (Nolte, et al. 2020)). Patients will be described with respect to

- Age
- Gender
- Medical history/comorbidities
 - o Diabetes mellitus
 - o Hypertension
 - o Hyperlipidemia
 - o History of coronary artery disease
 - o Heart failure
 - o Atrial fibrillation
 - o Previous history of stroke
 - o history of cancer
 - o smoking status
- acute therapy of ischemic stroke
 - o i.v. thrombolysis
 - o thrombectomy
- Physical examination
 - o Heart rate on admission
 - o systolic blood pressure on admission
 - o diastolic blood pressure on admission
- Current Medication
 - o Antiplatelet therapy
 - o dual antiplatelet therapy
 - o oral anticoagulation
 - o statin
 - o beta-blockers
- NIHSS
- mRS
- GRACE Score
- MoCA
- Creatinine
- Haemoglobin
- Peak troponin T

both overall and separately for presence/absence of dynamic troponin elevation and additionally for the presence/absence of ACS as well as for the diagnostic categories no ACS, MI Type 1 and MI type 2. Categorical data will be summarised by numbers and percentages. Continuous data will be summarised by mean, SD, median, IQR and range. Number of available observations and number of missing observations will be presented for the diagnostic groups (dynamic vs. stable) separately and overall for both groups. Differences in baseline variables between the two diagnostic groups will be analysed by appropriate tests, e.g. Chi-squared test, Mann-Whitney-U test, or analyses of variance.

5 Analysis

5.1 Analysis methods

5.1.1 Primary endpoint

The primary outcome analysis will be performed in the mITD population using the adjudicated endpoint data of the endpoint adjudication committee.

The presence/absence of ACS in relation to presence/absence of dynamic troponin elevation (defined as rise/falling pattern of >50% (Δ -change at 0 vs. 3 hrs)) will be analysed by calculation of the diagnostic odds ratio together with the 95%-confidence interval. Corresponding p-value will result from the likelihood ratio chi-square test.

5.1.2 Secondary endpoints

Secondary endpoint analysed are performed in an explorative manner without adjustment for multiplicity.

The secondary endpoints

- Mortality
- cardiovascular events (stroke, TIA, Myocardial infarction)
- MACE (combined endpoint of death, recurrent stroke, TIA, myocardial infarction)

are time-to event data. Event rates at 1 week, 3- and 12-months follow-up are reported based on Kaplan-Meier estimators. Cox proportional hazards will be used to estimate hazard ratios (95%-CI) comparing the diagnostic groups (stable vs. dynamic) for mortality and cause-specific hazard ratios for cardiovascular events taking death as competing event into account.

The secondary endpoint

- mRS (measured at baseline, 1 week, 3- and 12-months follow-up)

is an ordinal scaled score which ranges from 0 (no symptoms) to 6 (death). This endpoint will be analysed by fitting a proportional-odds logistic regression model to calculate the common odds ratio (95%-CI) as a measure of the likelihood that individuals in the stable group would lead to lower scores on the mRS scale than would patients in the dynamic group.

During the course of the study it turned out that the imaging procedure and count of hospital admission were not realisable. Therefore, these endpoints cannot be analysed.

Table 1 gives an overview of measurement time points of all endpoints.

Endpoints	Time point			
	V1 < 72 h after admission	V2 < day 7 days	V3 3-months FU	V4 12-months FU
Primary endpoint				
Acute coronary syndrome (ACS)			X	
Secondary endpoints				
Cardiovascular events (stroke, TIA, death, MI)			X	X
MACE (combined endpoint)		X	X	X
Mortality		X	X	X
mRS	X	X	X	X
MI Type 1 / MI Type 2			X	

Table 1: Frequency and scope of study visits

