Functional outcome will be assessed using the modified Rankin Scale (mRS) and the Lawton Instrumental Activities of Daily Living Scale (IADL). mRS will be assessed at V1, V2 and both telephone follow-up visits (see below). IADL will be assessed during telephone follow-up visits. The secondary endpoints recurrent myocardial infarction, recurrent cerebral ischemia (ischemic stroke or TIA) and mortality will be assessed at V2 as well as both telephone follow-up visits.

Follow-up:

Follow-up will be performed three and twelve months (\pm 14 days) after the index stroke in form of telephone interviews. During the telephone interviews, cognitive outcome and functional outcome will be assessed as described above. In addition, patients will be questioned on recurrent cardiovascular events (i.e. myocardial infarction, stroke and TIA). Data on mortality will be acquired from local registration offices.

Data management:

Data for the PRAISE study will be collected at each individual study site using an eCRF (electronic case report form). The PRAISE study will use the scientific infrastructure of the DZHK for data collection and storage. Data will be collected and stored according to the requirements of the data protection policy of the DZHK³² as well as Guidelines for Good Clinical Practice (GCP). Data will be stored using the webbased tool "secuTrial", which conforms with all regulatory standards of the FDA³². In case of participation in the DZHK biobanking, all biosamples will be stored locally in the recruiting study sites (see above).

The DZHK has a central data management (ZDM), which consists of three institutions

- Trusted third party (THS) at the Institute of Community Medicine, Greifswald
- Data repository (DH) at the Institute of Medical Informatics, Göttingen
- IT-administration at the DZHK main office

Medical data that are entered into the eCRF will be stored at the study database of the DH. The patients' personal data will be stored on the servers of the THS. Thus, the patients' personal data and the patients' medical data will be stored on separate servers provided by different organizations. Only the individual study sites will have access to both the patients' personal and medical data.

The THS will provide the eCRF for collection of patients' personal data via secuTrial. Thus, data will be stored directly on the servers of the THS. The signed informed consent (IC) form will be scanned and

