1.2 Objectives

The primary goal of the multicenter PRAISE study is to develop a diagnostic algorithm to better identify ACS as origin of troponin elevation in patients with an acute ischemic stroke. The primary hypothesis will test whether dynamic troponin levels (as compared to stable ones) indicate presence of ACS. The following hypotheses will be tested:

Primary hypothesis: A dynamic troponin elevation (>50% change at measurement after 3 hours) indicates an ACS in patients with an acute ischemic stroke. The change in troponin level (dynamic vs. stable after 3 hours) within patients with an acute ischemic stroke can be used to differentiate whether an ACS is present.

Endpoint: diagnosis of “ACS”, determined by an independent endpoint adjudication committee.

1. Secondary hypothesis: Stroke patients with dynamic troponin change have a worse functional outcome three or twelve months after the event in comparison to those with stable troponin.

Endpoints: Modified Rankin-Scale (mRS) after three and twelve months.

2. Secondary hypothesis: Stroke patients with dynamic troponin change have an increased risk for recurrence of cardiovascular events and a higher mortality rate in comparison to those with stable troponin.

Endpoints: Brain infarcts, transient ischemic attack (TIA), myocardial infarction (MI) and death as well as the combined endpoint thereof (MACE) during the acute inpatient stay, after three and twelve months.

In addition, in an exploratory approach we want to establish a combined rule-in/rule-out diagnostic algorithm to identify the subgroup of troponin-positive stroke patients in whom the diagnosis of ACS (i.e. type I vs. type II MI) vs. not is made by means of coronary angiography including stroke-specific cut-off values for troponin and other biomarkers, the value of ECG, echocardiography, clinical parameters, and combinations thereof.

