1.2.2 Main Secondary Outcomes

The secondary outcome parameters are defined as:

- Mortality (recorded at 1 week, 3- and 12-months follow-up)
- Cardiovascular events (new stroke, TIA, MI; at 1 week, 3- and 12-months follow-up)
- Combined vascular endpoint (MACE, i.e. mortality plus cardiovascular endpoints as above)
- Functional outcome (mRS; at baseline, 1 week, 3- and 12-months follow-up)
- Imaging (Stroke location and size, degree of cerebral white matter damage)
- New hospital admission

During the course of the study it turned out that the imaging procedure and count of hospital admission were not realisable. Therefore, these endpoints cannot be analysed.

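### SAP 5.1.2 reports stroke/TIA/MI rates by Kaplan-Meier although death competes with that endpoint; with deaths censored, the 12-month rates come out modestly too high (minor, descriptive rates only)

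*SAP*

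**What the plan says.** SAP 5.1.2 names three time-to-event secondary endpoints: mortality, cardiovascular events, and MACE. For all three, "Event rates at 1 week, 3- and 12-months follow-up are reported based on Kaplan-Meier estimators". No other estimator is given for any of these rates.

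In the text of 5.1.2, cardiovascular events are stroke, TIA and myocardial infarction. SAP 1.2.2 agrees: it lists mortality as a separate item, then "Cardiovascular events (new stroke, TIA, MI; at 1 week, 3- and 12-months follow-up", and then "Combined vascular endpoint (MACE, i.e. mortality plus cardiovascular endpoints as above". Death therefore belongs to MACE and not to the cardiovascular-event endpoint.

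The sentence in 5.1.2 that follows the Kaplan-Meier sentence plans Cox models, with "cause-specific hazard ratios for cardiovascular events taking death as competing event into account". This applies to the hazard ratio. The SAP does not say how deaths enter the reported rates.

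Table 1 of the same section labels the row "Cardiovascular events (stroke, TIA, death, MI", which puts death inside the list.

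**The concern.** Kaplan-Meier treats a censored patient as still at risk of the event later. A patient who has died is not. If deaths are censored, the curve estimates the risk in a hypothetical setting where nobody dies first, and its complement exceeds the proportion of patients who actually have a stroke, TIA or MI. A reader will take a 12-month event rate as that proportion.

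The cause-specific hazard ratio is valid with deaths censored, but planning it does not correct the rates printed beside it.

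The distortion is larger in the group with more deaths. The second secondary hypothesis in SAP 1.2 is that the dynamic-troponin group has higher mortality, so the two groups' rates would be affected unequally. At stake is one descriptive output of an exploratory secondary endpoint.

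**Working it through.** **Inputs.** The documents state no event rate, death rate or cumulative incidence, so there is no figure of theirs to reproduce. The rates below are assumptions: 12-month event risk (as one minus Kaplan-Meier) of 10, 15 or 20%, and 12-month mortality from 5 to 30%. From the documents come the time points (1 week, 3 and 12 months), the planned 203 analysed patients (SAP 2.3), and the 11/29 share with dynamic troponin used in the protocol's sample size calculation.

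**Formulas**, with constant hazards, time in years and deaths censored:

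- h1 = −ln(1 − event risk), h2 = −ln(1 − mortality)
- One minus Kaplan-Meier: 1 − exp(−h1·t)
- Cumulative incidence: h1/(h1+h2) × [1 − exp(−(h1+h2)·t)]

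**Worked case**, event risk 15%, mortality 10%, t = 1:

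- h1 = 0.1625, h2 = 0.1054, sum 0.2679
- One minus Kaplan-Meier = 15.0%
- Cumulative incidence = 0.1625/0.2679 × (1 − 0.85 × 0.90) = 0.6067 × 0.235 = 14.26%
- Excess = 0.74 percentage points

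**Excess at 12 months, in percentage points:**

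| 12-month mortality | Event risk 10% | 15% | 20% | Relative excess |
|---|---|---|---|---|
| 5% | 0.25 | 0.37 | 0.49 | 2.5% |
| 10% | 0.50 | 0.74 | 0.98 | 5.2–5.3% |
| 15% | 0.76 | 1.13 | 1.48 | 8.0–8.2% |
| 20% | 1.02 | 1.52 | 2.00 | 11.1–11.4% |
| 30% | 1.56 | 2.32 | 3.07 | 18.1–18.5% |

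The protocol excludes patients with a life expectancy under one year, a premorbid mRS above 3 or a large infarct, which makes the bottom row less likely.

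**Earlier time points.** For 10–30% mortality and 10–20% event risk, the excess is 0.03–0.23 points at 3 months and at most 0.0015 points at 1 week.

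**Early deaths.** These figures are not upper bounds. If half of the 12-month death hazard falls in the first month, the 12-month excess (event risk 10–20%) becomes 0.7–1.4 points at 10% mortality, 1.4–2.9 at 20% and 2.2–4.4 at 30%. At 3 months it becomes 0.12–0.79 points for 10–30% mortality.

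**Simulation.** In 4,000 simulated studies of 203 patients with event risk 15%, mortality 20% and complete follow-up, mean one minus Kaplan-Meier was 15.0% and the mean proportion with the event was 13.5%. The gap of 1.5 points agrees with the table.

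**Effect on the group comparison.** Let both groups have the same event hazard, so that one minus Kaplan-Meier is 15.0% in each. With mortality of 10% and 15%, the cumulative incidences are 14.3% and 13.9%, a difference of 0.4 points that Kaplan-Meier does not show.

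**Scale against sampling error.** 203 × 11/29 = 77 dynamic patients, leaving 126 stable. For a rate near 14%:

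- Standard error, dynamic group: √(0.14 × 0.86/77) = 4.0 points
- Standard error, stable group: √(0.14 × 0.86/126) = 3.1 points
- Standard error of the difference: √(0.14 × 0.86 × (1/77 + 1/126)) = 5.0 points

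**The case against.** The strongest reply is that this hardly matters. The rates are descriptive, the section is declared exploratory, and at 10% mortality the excess is well inside one standard error. MACE, which contains death, is reported at the same time points, and the group comparison uses a valid cause-specific hazard ratio. All of this stands, and it is why the point is minor. It does not make Kaplan-Meier the right estimator: the error has a known direction and does not shrink with sample size.

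Second, the SAP never says that deaths are censored, and it speaks of event rates, not of cumulative incidence. Both are true, so the conclusion is conditional on censoring. Censoring is, however, the normal Kaplan-Meier handling of an endpoint without death, and no alternative is stated.

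Third, the net bias of the published rate is unknown. Under Follow-up in the protocol, "patients will be questioned on recurrent cardiovascular events (i.e. myocardial infarction, stroke and TIA" by telephone, whereas "Data on mortality will be acquired from local registration offices". Events in patients who die before an interview may be missed, which lowers the rates. This also stands. The present point concerns the estimator only, and a possible error in the other direction is no reason to keep it.

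Fourth, Table 1 could be read as placing death inside the endpoint, which would leave no competing event. That reading makes the endpoint identical to MACE and contradicts both the 5.1.2 text and 1.2.2. The row may be no more than a list of components, like the one in SAP 1.2: "Brain infarcts, transient ischemic attack (TIA), myocardial infarction (MI) and death as well as the combined endpoint thereof (MACE".

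**Conclusion.** The concern holds, at minor severity. With stroke/TIA/MI defined without death and deaths censored, the Kaplan-Meier rates in SAP 5.1.2 overstate the cumulative incidence whenever deaths precede later events. The direction is firm. The size depends on assumed rates and, for the tabulated figures, on constant hazards: about 0.5–2.0 percentage points at 12 months for 10–20% mortality, more if mortality is higher or deaths cluster early, and little or nothing at the earlier time points. Only the descriptive rates of this one endpoint are affected; no test or hazard ratio changes.

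**What to change.** In SAP 5.1.2:

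1. Limit the Kaplan-Meier sentence to mortality and MACE.
2. Report stroke/TIA/MI by group at 1 week, 3 and 12 months as Aalen-Johansen cumulative incidence with 95% confidence intervals, taking death without a prior stroke, TIA or MI as the competing event. Show the mortality rates alongside, because a lower cumulative incidence in one group may only reflect more deaths there.
3. State whether a fatal stroke or MI counts as the event or as the competing death.
4. Reconcile the Table 1 label with the 5.1.2 text and 1.2.2.

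The Cox models and cause-specific hazard ratios stay as they are. Cumulative incidences for the single components are optional.

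The cost is one changed sentence, one added sentence and one table label. Deaths are already collected, and R and Stata are already listed in SAP 5.4. The change does not recover events missed in patients who die before a telephone interview; the report should state that limitation.
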